6.5 Diversity Supplement - Overall Study Design

The proposed research will investigate how social factors are associated with pediatric cervical spine injury (CSI) risk, post-injury care and functional outcomes. Our project will use two methodologies to gather data: (1) retrospective review of the electronic medical record and structured medical billing data prepared for the Pediatric Health Information System (PHIS) and (2) fixed-response telephone-administered questionnaire. The final products of this work will lay the groundwork for future studies to create targeted interventions for injury prevention and health care facilitation to improve functional outcomes for at-risk youth.

Children will be included if they were enrolled in the parent grant and sustained a CSI as confirmed by the study neurosurgeon. From the parent study, we will be able to obtain information about the type of CSI diagnosis and acute care interventions as related to the CSI. Our study will conduct an extended chart review for pediatric CSI patients to richly describe social factors present in CSI patients, to further ascertain acute care intervention information and resources at the time of discharge. Additionally, we will also request PHIS IDs to review medical billing data for the incident visit and any subsequent visit within 30 days of the incident visit. PHIS includes patients from over 45 children's hospitals, to which all study sites in the parent grant participates. We will compare CSI patients with the overall population of children in the United States (US) by utilizing census data. Census tract data will be obtained from the American Community Survey. We will retrieve the home zip code at the time of injury for each patient and link in several secondary data sources to capture the social and physical characteristics of the neighborhood/community environment.

In parallel, we will use validated survey tools to assess social factors, health care delivery and functional outcomes of children with CSIs. The child's parent or legal guardian will be contacted via telephone to participate in a fixed-response telephone-administered questionnaire. Social factors will be assessed utilizing the Protocol for Responding to and Assessing Patient's Assets, Risks and Experiences (PRAPARE) and functional outcomes will be assessed through the National Institutes of Health Common Funds Patient-Reported Outcomes Measurement Instrument System (PROMIS) tool. Healthcare utilization and needs will be assessed based on health care services received in the cognitive, physical and socioemotional domains by standardized responses adapted from National Health Interview Survey. Phone calls will be made at least 1 month after initial diagnosis. The time since injury will be collected and included in the analysis. The

surveys are expected to take 15 minutes, and families will receive monetary compensation for participation. We will also include in the analysis retrospective data collected during Aim 1 chart review that includes acute care interventions and discharge resources.

Diversity Supplement The activities for Aim 1 will be conducted under waiver of consent and the activities for Aim 2 will be conducted under waiver of written documentation of consent. This is a minimal risk retrospective chart review study with no therapeutic interventions. Legal guardians of eligible subjects will be given a Consent, Parental permission, and Authorization cover letter that provides information regarding the study and information that they will be contacted for a telephone follow-up observational assessment if their child sustained a CSI.

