[name] et al. will conduct this work at approximately 18 PECARN trauma centers and collect prospective observational data from EMS and ED providers regarding CSI risk factors for children who undergo emergency evaluation after blunt trauma and follow enrolled subjects for 28 days to determine CSI status. The study will occur in two phases: development (13,333 children; 240 children with CSI) and validation (8,889 children; 160 children with CSI). The study will also capitalize on the research infrastructure to conduct an Applied Cognitive Task Analysis (ACTA) and tool prototype testing that will inform the iterative tool design to ensure that the tool is useable by EMS and ED providers. With data from the development cohort, a useable clinical decision support tool will be constructed that achieves > 95% sensitivity, as well as adequate specificity (> 40%) in the prediction of CSI. Subsequently, [name] et al. will determine the performance characteristics of the tool in the independent validation cohort and in a cohort that has EMS provider observations. The ultimate output from this project will be a set of specifications for the Pediatric CSI Risk Assessment Tool that will include a validated clinical decision rule, validated tool designs and functions, and recommendations for implementation. An accurate, validated, and ultimately field-tested Pediatric CSI Risk Assessment Tool will safely limit unnecessary spinal precautions and radiographic testing for millions of children while helping identify those children who are truly at risk for CSI.

1 Study Summary

Cervical spine injuries (CSI) are serious, but rare events in children.^{1, 2} Spinal precautions (rigid cervical collar and immobilization on a longboard) in the prehospital setting

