6.2 Diversity Supplement Specific Aims

Our study aims to identify modifiable health care disparities that can be reduced through targeted interventions and has the Specific Aims below:

- Specific Aim 1. Determine social factors associated with pediatric CSI risk using census tract data from the American Community Survey and other geographic data.
- Specific Aim 2. Determine social factors affecting disparities in health care delivery, post-injury care management, and functional outcomes in children with CSIs via structured interviews.

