6.3 Diversity Supplement - Subject Eligibility, Accrual and Study Duration

Eligible participants will be identified by study staff. Patients will be enrolled in the study if they meet the following inclusion criteria:

- Enrolled in the parent grant and has a CSI as determined by the study neurosurgeon

CSI, the outcome of interest, is defined in the parent grant as vertebral fracture, ligamentous injury, intraspinal hemorrhage, or spinal cord injury (on either MRI or spinal cord injury without radiographic association) involving the cervical region of the spine (occiput to the 7th cervical vertebra including ligamentous structures attaching the 7th vertebra to the 1st thoracic vertebra). Presence of CSI will be determined by review of study site cervical spine imaging reports and through applicable spine surgeon consultation notes and phone follow-up. Children will be considered to have CSI if after cervical spine imaging and if applicable consultation with a spine surgeon; they are determined to have CSI. If imaging report diagnoses conflict with spine surgeon consultation, the treating spine surgeon will be contacted for clarification.

Our study will enroll all pediatric patients diagnosed with CSI identified in the parent grant for medical record review and will attempt telephone follow-up survey for each patient during the 24-month enrollment period of the supplement. The parent grant will identify at least 360 pediatric patients diagnosed with CSI following blunt trauma. Based on prior studies using similar methodology, we expect that at least half of these families will agree to participate in the follow-up survey.

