6.4 Diversity Supplement - Rational and Background

Injury is the leading cause of morbidity and mortality in children, and there are vast disparities within childhood trauma that are both multifactorial and poorly understood.¹¹⁰ Furthermore, there is a paucity of literature regarding the social factors related to pediatric cervical spine injury risk. The evidence for disparities within pediatric trauma patients is sparse and incomplete within the literature¹. Elucidating the specific social factors that are related to CSI risk and poor outcomes has the potential to inform new strategies in prevention and post-injury interventions for at-risk youth. Although pediatric CSIs are uncommon events, over 1300 new cases occur every year and the injuries contribute to significant morbidity and mortality.^{111, 112} Examining the role of social factors in pediatric CSI will fill two major gaps in the present literature: (1) While there is considerable evidence of racial and ethnic health disparities in the adult trauma literature,¹¹³⁻¹¹⁶ little is known about such disparities in children or about how social factors contribute to pediatric CSI risk and outcomes. African-American children have been independently identified as having increased morbidity, mortality and functional deficit after traumatic brain injury compared to equivalently injured Caucasian children.^{116, 117} Although these studies clarify the relationship between trauma and disparities in general, the focus of the studies was not pediatric CSI. (2) There is a paucity of literature that addresses the disparities in health care delivery and functional outcomes in children with CSIs. To our

knowledge, no researchers have prospectively examined how social factors are associated with pediatric cervical spine post-injury care and functional outcomes.

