6.11 Diversity Supplement - Data Analysis

This study has two methodologies for data analysis based upon the specific aims.

- Specific Aim 1. Determine social factors associated with pediatric CSI risk using census tract data from the American Community Survey and other geographic data.

Standard descriptive summaries (e.g. means and standard deviations for continuous variables such as age and percentage for categorical variables such as gender) will be used to summarize demographic variables. To analyze whether the distribution of social factors in the CSI population differs from that in the general population we will calculate a standardized incidence ratio based on population level data from the American Community Survey. The methodology compares the observed distribution of social factors in the study's CSI population to what would be expected in the general population based on a synthetic cohort from census data.

- Specific Aim 2. Determine social factors affecting disparities in health care delivery, post-injury care management, and functional outcomes in children with CSIs via structured interviews.

Univariate analysis using chi-square testing and multivariate logistic regression will be used to determine the association between social factors and inequities in healthcare delivery and functional outcome for children with CSI including school performance, accessibility of healthcare resources, ED visits, and unplanned readmissions.

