10.6 Inclusion of Women and Minorities

The proposed subject criteria were selected to represent the population of children who may be at risk for CSI and in whom there are not clinical guidelines for evaluation and management. The gender, race and ethnicity of the study cohort will be demographically

representative of children who experience blunt trauma and who are cared for at the participating study sites. The PHS Inclusion Enrollment Report represents the expected demographic breakdown of the study population by gender, race and ethnicity. There will be no sex/gender, racial or ethnic group excluded for any reason. As such, no outreach programs are proposed for the purpose of recruiting specific sex/gender, racial, or ethnic group members.

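### Diversity Supplement Aim 1 is worded as association with CSI risk, but its ratio compares cases from about 18 trauma centres with all US children, so site location and referral cannot be separated from risk.

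*Protocol*

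**What the plan says.** The aim, in Protocol section 6.2 and again in 6.11, is worded as risk: "Determine social factors associated with pediatric CSI risk using census tract data from the American Community Survey and other geographic data". Section 6.4 says what such findings are for: "Elucidating the specific social factors that are related to CSI risk and poor outcomes has the potential to inform new strategies in prevention".

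The cases are defined in section 6.3: "Enrolled in the parent grant and has a CSI as determined by the study neurosurgeon". They arise only at the parent study's sites; the Abstract says the investigators "will conduct this work at approximately 18 PECARN trauma centers".

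The comparator is national. Section 6.5 says: "We will compare CSI patients with the overall population of children in the United States (US) by utilizing census data". Section 6.11 names the statistic, "we will calculate a standardized incidence ratio based on population level data from the American Community Survey", and describes it as setting the observed distribution of factors in the study's "CSI population to what would be expected in the general population based on a synthetic cohort from census data".

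Section 10.6 claims, for gender, race and ethnicity, that the parent cohort will be demographically "representative of children who experience blunt trauma and who are cared for at the participating study sites". It does not claim that the cohort represents US children.

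Section 6.5 also says that each case's home ZIP code will be retrieved and linked to neighbourhood data. Neither 6.5 nor 6.11 says that this geography will be used to restrict or weight the reference population.

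**The concern.** A standardized incidence ratio carries information on risk when the expected count comes from the population that gave rise to the cases. Here the observed count comes from children who reached about 18 particular hospitals, and the expected count comes from all US children. If a social factor is more or less common among the children these hospitals draw on than in the nation, the ratio moves away from 1 even when the factor has nothing to do with CSI.

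A reader of the results could then take a feature of where the hospitals are, or of who is referred to them, for a risk factor. The Supplement intends its findings to inform prevention and targeted interventions, so the distinction matters for that purpose.

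**Working it through.** **Inputs.** At least 360 CSI cases (section 6.3). About 18 sites (Abstract). Reference: US children (sections 6.5 and 6.11). The Protocol gives no factor prevalences, alpha, power or precision for Supplement Aim 1, so there is no stated figure to reproduce. As a side check on case numbers, the pilot incidence of 1.8% (section 2.2) gives 13,333 × 0.018 = 240.0 and 8,889 × 0.018 = 160.0, matching the Abstract and totalling 400. The 360 is a floor with no stated derivation, so both counts are used below.

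**Null value of the ratio.** Let n be the number of cases, p_source the factor's prevalence in the population supplying the cases, and p_US its national prevalence.

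- Expected count as planned: E = n × p_US.
- Mean observed count with no association: n × p_source.
- Null ratio: (n × p_source) / (n × p_US) = p_source / p_US.

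This is 1 only if p_source = p_US. The algebra is for a ratio not standardised on site geography.

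**Illustration; every prevalence is an assumption.** The observed count is Binomial(n, null ratio × p_US), with p_US treated as known. A result is falsely high if its exact (Clopper-Pearson) 95% interval lies wholly above p_US, and falsely low if wholly below. The calculation is exact, without simulation. With n = 360:

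| p_US | Expected count | High if count ≥ | Low if count ≤ | Falsely high, null ratio 1.00 | Falsely high, 1.10 | Falsely low, 0.90 |
|---|---|---|---|---|---|---|
| 10% | 36 | 49 | 24 | 1.7% | 7.0% | 6.8% |
| 15% | 54 | 69 | 40 | 1.9% | 10.0% | 10.4% |
| 20% | 72 | 88 | 56 | 2.3% | 14.6% | 12.6% |
| 30% | 108 | 126 | 90 | 2.3% | 22.6% | 21.4% |

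At p_US = 15%, a null ratio of 1.20 gives 30.2% falsely high and 4/3 gives 67.4%; a null ratio of 0.80 gives 33.7% falsely low and 2/3 gives 78.8%.

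With n = 400 and a null ratio of 1.10, the falsely high rates at the four prevalences are 9.0%, 12.7%, 15.3% and 24.4%. More cases make the false signal more frequent, because the shift is a bias and not sampling error.

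**The case against.** Four counter-arguments deserve weight.

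*The condition is not shown to hold.* Nothing in the Protocol shows that the children these sites draw on differ from US children on any social factor. Section 10.6 covers gender, race and ethnicity in the parent cohort; not claiming national representativeness is not evidence of a difference. This stands. A reader might infer that Aim 1 will produce biased results for particular factors; the documents do not support that.

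*The ratio is standardized, and the details may be in the statistical analysis plan.* A synthetic cohort standardised on site geography would have a different null value. This limits the algebra to the case stated. But the text names US children and the general population as the reference, so a plan that substituted a catchment reference would contradict section 6.5.

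*Section 6.11 asks only whether the distributions differ.* For that descriptive question the comparison is sound. The difficulty is that the same bullet, and section 6.2, present the answer as association with CSI risk.

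*A catchment reference does not cure the problem.* Children living near a site may be taken elsewhere, and injured children reach trauma centres selectively, so the census prevalence of an area is still not the prevalence in the source population. It also removes between-area differences, which an aim built on census-tract data may be seeking. Both points stand, and it would be wrong to present a site-area ratio as a clean estimate of risk. It removes one known mismatch and should be reported with its limits.

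**Conclusion.** As the Protocol is written, Supplement Aim 1 can describe how enrolled CSI cases differ from US children. It cannot by itself support a statement about CSI risk, because a ratio away from 1 could reflect site location or referral. That conclusion rests on the text of sections 6.2, 6.3, 6.5 and 6.11 and on the ratio not being standardised on site geography.

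The size and direction of any bias are unknown, and where the prevalences agree there is none. The error rates above show only what a mismatch of a given size would do; they are not estimates for this study.

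A reader might also infer that the decision rule is affected. It is not: derivation and validation in the parent study do not use this comparison. Severity is minor to moderate.

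**What to change.** Amend sections 6.5 and 6.11, and carry the same wording into the statistical analysis plan:

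1. State that the comparison with US children describes how enrolled CSI cases differ from them and is not by itself evidence on CSI risk.
2. Add a second ratio whose expected counts come from American Community Survey data for the areas the sites serve, weighted by each site's share of CSI cases. Set the catchment and transfer rule before analysis, apply it alike to observed and expected counts, and report both ratios.
3. State that the second ratio removes the location mismatch but not selective referral to these hospitals, and that it also removes between-area differences, so any statement on risk carries those limits.

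The cost is wording, one more census extract, and the work of defining a catchment for each of about 18 sites; home ZIP codes are already to be retrieved. The number of cases touched by a transfer rule is unknown: in the pilot 953 of 4,091 children (23.3%) were transferred in (section 2.2, Table 2), but that covers all pilot children, not those with CSI.

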6.6 Diversity Supplement - Subject Identification

Subjects for this study will be identified using resources from the parent grant. The eligibility criteria, data collection activities and consent methodologies for each aim are explained below.

- Aim 1. Children with CSI will be identified by the parent grant Data Manager (reference Section 1.2 of the parent grant eligibility criteria). The Data Manager will provide each participating site a list of subject ID's for those children with CSI. These will be the subjects for which we perform a limited chart review and request PHIS participant ID's.
- Aim 2. Subjects from Aim 1 that are conversant in English or Spanish will receive a Consent and Authorization Cover Letter from the study management team at the DCC. This list of subjects will be sent to a limited group of study personnel at Nationwide Children's Hospital ([name], [name] and a research coordinator (RC)). If a legal guardian contacts the study management team at the DCC to opt out, they will not be contacted by the team at Nationwide Children's for the telephone follow-up. Figures 6 and 7 represent two consent methodologies for the study

[figure not shown]

Figure 6: Consent Procedures for Study Population

6.7 Diversity Supplement - Study Workflow

This study contains two data collection methodologies conducted under separate consent procedures based on the respective specific aim.

Aim 1. Medical Record Review conducted under waiver of consent

- The parent grant Data Manager will identify subjects with adjudicated CSI.
- The research staff at each study site will perform a limited medical record review for subjects with adjudicated CSI and provide the requested PHIS ID's for the incident visit and any visit within 30 days of the incident visit.

Aim 2. Telephone Follow-up Assessment conducted under waiver of written documentation of consent

- Based upon the limited medical record review, parents/guardians conversant in English or Spanish will be eligible to receive a cover letter.
- The DCC will mail consent the Consent, Parental permission, and Authorization cover letter to the family.
- Eligible parents/legal guardians who are sent a cover letter will be contacted at least 30 days post-ED enrollment by [name] or RC to complete the Phone Consent form unless the parent/legal guardian chose to opt out.

[figure not shown]

Figure 7: Study Workflow and Consent Procedures

6.8 Diversity Supplement - Medical Record Review

The parent grant Data Manager at the Data Coordinating Center (DCC) will identify eligible subjects based on CSI adjudication. They will provide a list of participant ID's for eligible subjects to each study site. The site will complete a supplemental demographic form (limited medical record review) and submit the PHIS ID's to REDCap. All participating study sites prepare and submit billing data to PHIS.

Each study site will use REDCap, and the data will be securely collected at different locations but managed within the same system at the DCC. REDCap protects PHI through filters to limit access to identifiable information. For example, only key study personnel (study PI and parent grant Data Manager) and site-specific research team members only have access to their site's data which are not deidentified. Data management for PHIS medical billing data will be conducted centrally at Nationwide Children's Hospital, the lead study site, by the Nationwide Children's Hospital PHIS Data Manager. For the medical billing data, patient encounters will be assigned a unique study identification number by PHIS that will be associated with the study participant number. A deidentified dataset will be used for statistical analyses. The electronic data will be deleted within seven years following the last publication stemming from the study.

6.9 Diversity Supplement - Telephone Follow-up Assessment

Legal guardians of patients with CSI who have been identified as conversant in English or Spanish will be mailed a Consent, Parental Permission, and Authorization Cover Letter. This cover letter provides information regarding the study and information that they will be contacted for a telephone follow-up assessment. This cover letter will also include instructions for how to opt out of telephone follow-up. Unless the legal guardian has contacted the Project Manager at the DCC and elected to opt out of the telephone follow-up, they will receive a phone call from either [name] or a RC at least 30 days after

ED enrollment into the parent study. At the beginning of this call, the interviewer will explain the study and obtain verbal consent. At this time, the legal guardian can decline participation or continue with the phone interview. If participation in the phone interview is declined, all subsequent attempts for contact and recruitment will be terminated. If the legal guardian consents to participation, the interviewer will administer a structured questionnaire that assesses the patient's demographics, functional outcome, resources needed upon discharge and ongoing healthcare needs.

If initial telephone attempts to contact the legal guardian are unsuccessful, subsequent attempts will be limited to three total attempts. If voicemail is encountered, we will leave a message and callback information for the legal guardian to assist with arranging follow-up. If the telephone number is a disconnected line, all subsequent attempts for contact to that telephone number will be terminated. Our final attempt to contact a family for telephone follow-up will be a mailed letter notifying them that attempts to contact for participation in the survey had been made, provide contact information should they want to participate and confirm no further contact will be attempted.

For time and inconvenience, legal guardians will receive \$50.00 for completing the phone interview. Funds will be issued on a debit card specially designed for clinical research, ClinCard. The ClinCard Research Stipends Payment System is designed to deliver electronic payments to program participants for time associated with clinical trials. In order to process the payment, we will need to verify their mailing information, patient's name and date of birth, legal guardian's name, and telephone number. When the interview is completed, funds will be approved, automatically loaded onto the card and mailed to the legal guardian's home address.

We selected 30 days for telephone follow-up because previous studies demonstrated that patients with CSI missed on their initial visit are usually diagnosed within 3 weeks of injury.^{108, 109} PECARN has used this method of identifying missed injuries in previous studies.^{92, 96, 97} Additionally, a benchmark for care per the Centers for Medicare and Medicaid Services is the 30-day readmission rate, therefore we plan to gather information within 30 days of the initial ED visit. Finally, this would give enough time for eligible subjects in the parent grant to complete the adjudication process for CSI.

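### Diversity supplement, Aim 2: the 30-day window for readmissions and return ED visits starts at the ED visit, not at discharge, and the data source is not named

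*Protocol*

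**What the plan says.** Section 6.11 names the Aim 2 outcomes, among them "school performance, accessibility of healthcare resources, ED visits, and unplanned readmissions". On method it says: "Univariate analysis using chi-square testing and multivariate logistic regression will be used".

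The window is described in three places.

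- Section 6.9, explaining the choice of 30 days, refers to a benchmark that "is the 30-day readmission rate, therefore we plan to gather information within 30 days of the initial ED visit".
- Section 6.5 says that PHIS IDs will be requested in order to "review medical billing data for the incident visit and any subsequent visit within 30 days of the incident visit".
- Section 6.7 tells sites to "provide the requested PHIS ID's for the incident visit and any visit within 30 days of the incident visit".

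None of these mentions discharge. On the interview, section 6.5 says "Phone calls will be made at least 1 month after initial diagnosis", and sections 6.7 and 6.9 put the call at 30 days or more after ED enrollment. No upper limit is given. The only time variable that section 6.5 brings into the analysis is time since injury.

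**The concern.** A readmission cannot happen before a discharge, and a child who is still an inpatient cannot make a return ED visit. If the 30 days run from arrival, a child sent home from the ED has the whole window at risk, a child admitted for two weeks has about half of it, and a child in hospital for 30 days has none. The outcome would then partly measure how long the first stay lasted.

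Aim 2 asks whether social factors are associated with care and outcome after injury. If a social factor is also associated with length of stay, the longer-stay group has less opportunity to show an event, and part of the estimated association comes from the window. If there is no such link, the main loss is of events in a small sample: section 6.3 expects at least 360 children with CSI and at least half of families (360 × 0.5 = 180) in the survey.

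The collection window is fixed in the protocol. An analysis plan could redefine the outcome, but it could not recover billing visits that were never requested.

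**Working it through.** The protocol gives no readmission rate, length of stay or power calculation for these outcomes, so there is no figure of its own to reproduce. The check has two parts.

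**1. Days at risk.** Inputs: a 30-day window counted from the initial ED visit (6.9), and the fact that a readmission must follow discharge.

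Days at risk = max(0, 30 − length of stay).

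**2. What that does to an observed proportion.** Assumptions, not in the protocol: a constant daily hazard after discharge, and a true 30-day post-discharge risk R of 5%, 10% or 15%.

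Observable risk = 1 − (1 − R)^(days at risk / 30).

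| Stay (days) | Days at risk | R = 5% | R = 10% | R = 15% |
|---|---|---|---|---|
| 0 | 30 | 5.0% | 10.0% | 15.0% |
| 3 | 27 | 4.5% | 9.0% | 13.6% |
| 7 | 23 | 3.9% | 7.8% | 11.7% |
| 14 | 16 | 2.7% | 5.5% | 8.3% |
| 21 | 9 | 1.5% | 3.1% | 4.8% |
| 28 | 2 | 0.3% | 0.7% | 1.1% |
| 30 or more | 0 | 0% | 0% | 0% |

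Take two groups with the same true risk of 10% that differ only in length of stay.

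- 14 v 3 days: (0.0546/0.9454) ÷ (0.0905/0.9095) ≈ 0.58.
- 21 v 3 days: (0.0311/0.9689) ÷ (0.0905/0.9095) ≈ 0.32.

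The true odds ratio is 1 in both cases. The 14 v 3 day figure depends little on R: about 0.59 at R = 5% and 0.57 at R = 15%. These comparisons put every child in a group at one stay, so they illustrate the mechanism and do not estimate the bias in this study.

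**With the clock started at discharge**, every child has the same nominal 30 days, the observable risk equals R at any length of stay, and both odds ratios return to 1.

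**Does anything else in the protocol restore the lost days?** Time since injury (6.5) is not time since discharge; two children with the same time since injury can have very different days at risk. Length of stay and person-time are not mentioned. Adjusting for stay later would not help children with stays of 30 days or more, for whom no event could be recorded in this window.

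**The case against.** The strongest reply is that the protocol never says the readmission variable comes from billing data. Aim 2 is framed around structured interviews, the PHIS request sits under Aim 1 (6.6, 6.7), and section 6.5 names only acute care interventions and discharge resources as the Aim 1 data carried into Aim 2. Section 6.5 also places healthcare utilization in the telephone questionnaire. Calls have no latest date, so an interview could pick up events after day 30, including in long-stay children. For an interview outcome, time since injury would be partly relevant, since the date of the call sets how far back the family can report.

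This stands as a limit on the point but does not remove it. Section 6.11 names no source, and no post-discharge window is defined for the interview. With calls at any time after 30 days, follow-up after discharge would be unequal there too.

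Second, section 6.9 explains timing and does not define an outcome, and the incident visit in 6.5 and 6.7 could mean the whole hospital stay, since 6.8 describes PHIS data by encounter. That reading is possible. Even so, 6.9 says the initial ED visit, and sites could apply the terms differently.

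Third, detailed endpoint definitions often belong in the analysis plan. That is fair for the denominator and for handling transfers, but not for the span of billing records that sites are told to supply.

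A reader might go further and infer that later return visits are never captured, or that long-stay children will look falsely good and a disparity will be hidden or reversed. The protocol does not support this. The first is shown only for the PHIS request. The second needs a link between length of stay and social factors, which the protocol does not report.

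**Conclusion.** The point holds in a limited form. The protocol cites a readmission rate as a reason for its window, starts that window at the initial ED visit in 6.9, and uses an unreconciled term for the billing request in 6.5 and 6.7. On the ED-visit reading, billing data under-count readmissions and return ED visits in long-stay children, down to none for stays of 30 days or more. That follows from arithmetic and needs no outside definition of the benchmark.

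Whether the Aim 2 associations are distorted, in which direction and by how much, depends on how length of stay varies across social factors, and that cannot be computed from the document. If stays are similar across social groups, the main effect is a lower event count. Differing stays are plausible: the CSI definition includes spinal cord injury, and section 8.1 names children needing surgical stabilization as a group. Plausibility is all the protocol offers.

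The matter concerns two of the outcomes listed for one supplement aim and leaves the parent study's derivation and validation aims untouched. It should still be corrected, because unrequested billing visits cannot be restored at analysis.

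**What to change.** - In sections 6.5, 6.7 and 6.9, use one term and one start: 30 days from discharge from the incident encounter, with ED discharge as the start for children not admitted.
- Request PHIS IDs for all visits up to that date.
- Restrict the denominator for readmissions and return ED visits to children discharged alive, and report separately those who died or were still in hospital.
- In section 6.11, state whether these outcomes come from PHIS or from the interview, and apply the same post-discharge window to either. If the interview is used, the call must fall after that window closes.

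The cost is a slightly later and longer PHIS request for admitted children, and a matching update to the consent and HIPAA waiver wording in section 6.12, which may need IRB review. PHIS data are already handled by encounter (6.8), so the billing change needs no new contact with families. If the interview is the source, some calls to families of long-stay children would move later.
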